6. STUDY PARTICIPANTS

6.1. Inclusion Criteria:

- Participants must be admitted to the Manchester University NHS Foundation Trust or have attended an outpatient appointment, as a patient or relative/carer/partner, at the Manchester University NHS Foundation Trust
- Participants must have capacity to independently consent
- Patients must be over the age of 18 years.

6.2. Exclusion Criteria:

- Patients unable to independently consent
- Patients under the age of 18

6.3. Recruitment:

As outlined above (section 5.2), recruitment will take place in 2 locations at a single site. The recruitment approach will differ slightly between IPTIP-I and IPTIP-O. All patients will be asked to consent to the following:

- Blood sampling for DNA extraction or saliva sampling for DNA extraction (if
 difficulties in obtaining a blood sample as first choice) or access to stored DNA where a
 sample has already been taken for a previous clinical indication.
- 2. Access to inpatient prescribing data
- 3. DNA analysis related to pharmacogenetics
- 4. Sharing of identifiable data with Graphnet CareCentric, who operate the Greater Manchester Care Record (GMCR), to allow data retrieval from primary care records.
- 5. Access to historical and future healthcare data via the Greater Manchester Care Record (GMCR)
- 6. Transfer from the Greater Manchester Care Record (GMCR) into the NHS GM Analytics and Data Science Platform (ADSP) for analysis and storage for a maximum of 5 years after the end of the IPTIP study.
- 7. Where access to the GMCR is not possible, because the patient is not registered with a General Practitioner in Greater Manchester, permission will be sought to access prescribing history via the Summary Care Record (SCR).
- 8. Sharing of anonymized data and patient samples for ethically approved research.
- 9. Patients will have the **option** of consenting for a buccal sample (cheek swab) to be taken alongside the blood or saliva sample. This will be used to assess whether it is possible to test for the pharmacogenetic variants more quickly using a non-invasive sample.

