6.3.1. IPTIP-I Recruitment

The acute medical unit (AMU) at the Manchester University NHS Foundation Trust (MFT) is 48 bedded unit. This represents one of several acute wards at the Manchester Royal Infirmary. Recruitment will take place in one of three wards (AMU, Manchester Vascular Centre, and the Acute Care Unit) — ensuring a diverse cohort of patients are recruited. Each day during the recruitment period a randomised list of the beds across the three wards will be generated, and the patients will be approached in this order, minimising sampling bias to avoid the sample being skewed towards those more amenable to recruitment such as the young or English speaking. This approach will endeavor to ensure that individuals across all age groups, both sexes and all ethnicities are included. Every month, average participant demographics will be compared against existing control data to ensure a representative sample of the inpatient population is being recruited. The patients will be approached by the direct clinical or research team (CRN research support and sub-investigators), the study will be discussed and a PIL will be provided. Thereafter, if the patients wish to enrol, a

consent form will be signed, blood or saliva (+/- buccal) samples for DNA extraction will be taken and the initial recruitment proforma will be completed, generating a unique study ID.

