6.3.2. IPTIP-O Recruitment

The MCGM serves a population of 5.7 million and there are over 10,000 appointments each year. Participants will be recruited from the MCGM outpatient department, a dedicated unit where a clinic room will be reserved for IPTIP recruitment. Anyone attending the MCGM, including the consultee and their relatives, carers or partner, will be eligible for recruitment, within the scope of the exclusion criteria as described above (Sections 6.1 and 6.2). Participants will be identified by the reviewing clinician in clinic, or by writing to patients who have previously been seen in the department and are still under follow up with the clinical genetics service. As a result of the COVID-19 pandemic, there is an approximately 50:50 split between face-to-face and virtual clinic appointments. As such, we propose both face-to-face and virtual consenting processes, to facilitate recruitment and ensure those who cannot travel as easily are not prevented from participating. For face-to-face appointments, interested individuals will be invited for a discussion with the research team in the reserved consultation room and the study will be discussed, during which a PIL will be provided. If patient's wish to have more time to consider the study, they will be offered a follow up telephone or videocall. Where patients wish to enroll during clinic, a consent form will be signed, blood/saliva samples for DNA extraction will be taken (if a stored sample not already available) and the initial recruitment proforma will be completed, generating a unique study ID.

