For virtual appointments or where patients indicated they would like more time to consider the trial, a telephone or video call (NHS Attend Anywhere or Microsoft Teams) will be arranged with the research team to discuss the study. Following this phone call if the patient is happy to receive information about the study, an information sheet and consent form will be posted to the participant with a pre-addressed return envelope. A short data collection form will be included with the consent form for patients to complete. This will allow accurate collection of demographic and drug allergy information, which would usually be completed as part of the initial recruitment proforma, if the patient was seen in a face to face clinic. If the patient wishes to participate, then they can return the completed consent form and data collection sheet in the pre-addressed return envelope. The contact details for the research team are on the patient information sheet should the patient wish to discuss the study with a member of the team after reading the patient information

sheet. If a DNA sample is already available then this will be accessed for the study, otherwise an appointment will be made for the patient to have their bloods taken for DNA extraction or a saliva sample will be sent in the post for completion and return. Where patients are contacted by letter to inform them about the trial, they will be offered a virtual consultation or a face to face appointment at their convenience.

If a patient has been sent the study information and has not returned a completed consent form after one month, then the research team may make contact with the patient to see if they are still interested in participating in the study and re-send the study information if required.

Each month, average participant demographics will be compared against existing control data to ensure a representative sample of the population attending the MCGM is being recruited. This data will then be fed back to the recruiting clinicians facilitating more tailored recruitment. Information regarding the trial will be placed on the North West Genomic Medicine Service Alliance (GMSA) website. This will be patient facing material (Appendix 2) which will provide information on the study and advise how interested participants can become involved.

6.4. Participants who withdraw consent:

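### IPTIP-O aims to represent MCGM attenders but has no random or consecutive approach order and no record of recruitment route, so its proportion may carry selection bias that the 5-point margin does not cover

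*Protocol*

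**What the plan says.** **IPTIP-O (protocol section 6.3.2).** Three routes lead into the arm.

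- Clinic and letter: "Participants will be identified by the reviewing clinician in clinic, or by writing to patients who have previously been seen in the department". The letters go to people still in follow-up with clinical genetics. Nothing states which attenders are to be identified, or whether all or only some follow-up patients are written to.
- In face-to-face clinics, interest comes before contact with the study team: "For face-to-face appointments, interested individuals will be invited for a discussion with the research team in the reserved consultation room".
- Material on a regional genomics website is to "provide information on the study and advise how interested participants can become involved".

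The same section sets the aim of a sample that represents those attending the MCGM. It relies on a monthly comparison of average demographics with control data, and adds: "This data will then be fed back to the recruiting clinicians facilitating more tailored recruitment".

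**IPTIP-I (section 6.3.1).** Here there is a rule: "Each day during the recruitment period a randomised list of the beds across the three wards will be generated". Patients are approached in that order, with the stated purpose of "minimising sampling bias to avoid the sample being skewed towards those more amenable to recruitment". The monthly demographic comparison applies to this arm too.

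**Use of the result.** Section 7 defines the primary outcome as the proportion with a genotype related to a current or past medicine, reports it by recruiting site, and intends it for national policy. Section 9.1 compares the two arms on it by chi-square. Section 9.2 sizes each arm at 323 for a precision of 0.05.

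**Recorded data (section 8.1).** The list for initial collection includes recruiting site but not the route by which a participant came in.

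**The concern.** The protocol recognises, for inpatients, that an uncontrolled order of approach can skew a sample, and guards against it. For outpatients it sets the same aim of representativeness without an equivalent guard.

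The primary outcome needs two things: an actionable genotype and exposure to the related medicine. Genotype is unlikely to influence who is identified or who volunteers. Medicine exposure could, because people who take more medicines, or have had trouble with one, may be more or less inclined to join a pharmacogenetic study. Two samples with the same average age and sex can still differ in medicine use, so the demographic check does not settle the matter.

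Two results are at stake: the IPTIP-O proportion as a measure of utility in that setting, and the IPTIP-I versus IPTIP-O test, which could pick up a difference in how people were sampled rather than a difference between settings. A larger sample would not remove either problem.

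**Working it through.** **1. The plan's own figure.** Inputs from section 9.2: Z = 1.96, P = 0.30, e = 0.05.

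n = Z² × P × (1 − P) / e² = 3.8416 × 0.21 / 0.0025 = 322.69, rounded up to 323 per arm and 646 in total. Both match the protocol. The half-width at 323 is 1.96 × √(0.21 / 323) = 0.04998. This margin describes random error under simple random sampling and contains nothing for selection.

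**2. How much selection would matter.** The documents give no participation rates, so this step is an assumption. Let k be the chance of entering the sample for a person with the outcome, divided by the chance for a person without it. With a true proportion of 0.30:

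expected observed proportion = 0.3k / (0.3k + 0.7)

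| k (assumed) | Observed | Bias | Coverage of true 0.30 by the 95% CI | Chance of a significant arm difference in the direction of the bias |
|---|---|---|---|---|
| 1.1 | 0.33 / 1.03 = 0.320 | +0.020 | 88% | 8% |
| 1.25 | 0.375 / 1.075 = 0.349 | +0.049 | 55% | 26% |
| 1.5 | 0.45 / 1.15 = 0.391 | +0.091 | 8% | 69% |

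Coverage uses the normal approximation at n = 323. For k = 1.25 the standard error is √(0.349 × 0.651 / 323) = 0.0265, the bias is 0.0488 / 0.0265 = 1.84 standard errors, and coverage is Φ(1.96 − 1.84) ≈ 55%. The last column assumes 323 per arm, a true 0.30 in both arms and no selection in IPTIP-I.

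**3. The selection that uses up the whole margin.** Solving for an observed 0.35: k = (0.35 × 0.70) / (0.30 × 0.65) = 0.245 / 0.195 = 1.26. Solving for 0.25: k = (0.25 × 0.70) / (0.30 × 0.75) = 0.175 / 0.225 = 0.78. Fairly modest selection in either direction is enough.

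**4. Whether the safeguard reaches it.** The section 8.1 list holds date of birth and sex, but not ethnicity. Matching averages on such variables leaves k unconstrained within each age and sex group. No log of people approached and declining is described, and no route field is listed, so the recorded data offer no direct way to estimate k or to compare routes.

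**The case against.** Much can be said for the plan. Both arms consist of people who consent, and a random bed order decides who is asked, not who agrees. Section 6.3.2 makes anyone attending the MCGM eligible, the letters have a defined frame, and the feedback to clinicians is meant to keep the sample representative. Section 8.3 says no individual results go back to participants or clinicians, which weakens the motive for a person with a medicine problem to join or for a clinician to steer one in. All of this stands, and it limits the point.

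It also rules out several stronger readings.

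- *The arm is biased upwards.* A reader might infer enrichment for people with medicine problems. The documents do not show it. Relatives, carers and partners are eligible and could lower the proportion, so the direction is open.
- *Clinicians hand-pick patients.* The text says they identify participants. Discretion is only an inference from the absence of a rule.
- *A volunteer from any clinic in the Trust can join IPTIP-O.* Section 6.1, which asks for someone who has "attended an outpatient appointment, as a patient or relative/carer/partner" at the Trust, reads that way alone. But it covers both arms, and sections 5.1 and 6.3.2 confine IPTIP-O to the MCGM. This is loose wording, not evidence of bias.
- *Route can never be examined.* Section 8.1 lists initial collection, and postal consent leaves its own trace. Still, web or letter origin is not captured as such.

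What the objection does not answer is the missing approach order, measured against the protocol's own aim and its own practice in the other arm. An unseen SAP may plan analyses by route, but it can use only what was recorded at recruitment.

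**Conclusion.** The point holds as a cheap improvement. Section 6.3.2 states an aim of representativeness without a sampling rule that supports it, and its only check does not touch medicine exposure. The IPTIP-O proportion is not assured to estimate the proportion among MCGM attenders, and the comparison of arms may partly reflect different recruitment. It would go too far to say that the estimate is wrong or too high.

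The size is unknown. The ratios of 1.26 and 0.78 that would consume the 5-point margin rest on the assumed selection model and on the protocol's P of 0.30. They show how sensitive the result is, not how large the bias will be. The figure of 323 is correct as calculated.

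**What to change.** - **Section 6.3.2:** approach clinic attenders, and send letters to follow-up patients, in random or consecutive order from the existing MCGM clinic and follow-up lists.
- **Section 8.1:** add one field for recruitment route (clinic, letter, web or self-referral).
- **Reporting:** give the IPTIP-O primary proportion by route, with a sensitivity analysis that leaves out self-referred participants. They need not be dropped from the main result, since some may be current MCGM patients and so belong to the target population.
- **Section 6.1:** align the wording with 5.1, so that IPTIP-O requires MCGM attendance or follow-up.
- **Monthly demographic comparison:** keep it as monitoring.

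The cost is some extra list handling, one proforma field and possibly slightly slower IPTIP-O accrual. The sample size stays at 323. An approach order does not remove bias from refusal, so some selection will remain in both arms.

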7. OUTCOME MEASURES

The Primary outcome is the proportion of patients with a genotype related to a medicine they are currently, or have previously been, prescribed. Genotype-phenotype relationships will be assigned where there is high level PharmGKB evidence for clinical actionability (Levels 1A or 1B). Rates for the whole cohort will be presented but will be split by recruiting site and by age. These measures will be used to quantify the potential clinical utility of pre-emptive PGx testing in different settings, directly informing policy decisions around the implementation of PGx nationally.

In addition to the primary outcome, baseline characteristics will be presented. Medicine exposure by British National Formulary (BNF) class will be presented with sub-analysis by age group, sex, and the presence of recorded co-morbidities. Analysis will be presented for the whole cohort, and separately for inpatient and outpatient arms.

Genotype and metaboliser frequencies, derived using CPIC guidelines, will be presented for the whole cohort. These frequencies will then be analysed by age, sex, and ethnicity. Analysis will be presented for the whole cohort, and separately for inpatient and outpatient arms. Statistical differences in genotype based on demography, or recruiting site, will be tested via ANOVA or independent t-test. Genotype frequencies will be compared against an independent control cohort, generated as part of an ongoing trial, genotyping 1500 patients from the TARDIS Trial.²⁵ This will allow for comparison as to whether the dataset generated in this fellowship is consistent with others around the country, so clarifying generalisability.

Finally, the predictive value of patient variables, such age, co-morbid status, or ethnicity, for exposure to medicines where pharmacogenetic guidelines exist will be determined. This will be used to assess whether these variables, either in isolation or in combination, could be used to define a targeted screening approach for pharmacogenetics.

8. DATA COLLECTION, SOURCE DATA AND CONFIDENTIALITY

8.1. Data Collection at Recruitment

An online recruitment proforma will be completed for each participant by the study team, which will assign the participant with a unique study ID. This online proforma will be part of a bespoke electronic study tool, developed in the MCGM for this study by a web-developer ([name]). This will provide the study team with access to an online recruitment portal. This online tool will be hosted on Manchester University NHS Foundation Trust Servers and will only be accessible within the trust via the intranet (Internally facing). The system builds on existing informatic architecture and will be subject to all legal requirements as outlined by the General Data Protection Regulation (GDPR) and set by the Medicines and Healthcare products Regulatory Agency (MHRA). Initially, the study team will be asked to collect the following details.

- 1. Name
- 2. Date of Birth

- 3. Sex
- 4. NHS Number
- Recruiting site
- 6. Allergy status
- 7. Admission Date (IPTIP-I arm only)
- 8. Participant Reported Current Medicines (IPITIP-O arm only)

8.2. Sample Collection, Storage and Genotyping

The information gathered at recruitment will be sufficient for the electronic platform to generate a study ID, allowing 3ml of EDTA blood or 2ml of saliva to be taken and labelled with the IPTIP study ID only. Blood or saliva samples will then be transported to the Manchester Centre for Genomic Medicine via existing and secure clinical pathways for internal specimen transport. There, DNA will be extracted and quantified by the North West Genomic Laboratory Hub (NW-GLH), an NHS ISO15189 accredited laboratory. DNA samples will be labelled with the Study ID and stored at -20°C until genotyping. Where DNA samples are available, an aliquot of DNA will be transferred from the DNA archive to the -20°C study freezer and labeled with the Study ID only. If a saliva sample has been completed at home by the participant, it will be returned in a pre-printed freepost envelope marked UN3373 to the genetics research office, after which it will be labelled with IPTIP ID only and delivered to the NW-GLH laboratory for DNA extraction as detailed above. Where buccal samples are collected, these will be labeled with the patient's study ID after collection and transferred to the NW-GLH for storage (as above).

Genotyping will be undertaken using the Agena[™] iPLEX PGx 74 assay. This pre-designed assay targets frequent and clinically relevant variants across 20 pharmacogenes. This is a 3-well assay, but a 4th will be added for CYP2D6 copy number variants. To assess the analytical performance of the Agena[™] platform against other pharmacogenetic systems, a proportion of the samples will be tested in parallel on an additional pharmacogenetic platform. These additional platforms will not test variants other than those already on the Agena[™] iPLEX PGx 74 platform. With donor consent, anonymized samples will be kept beyond the completion of the study for future ethically approved

research. Buccal samples collected as an optional extra sample type for a sub-set of patients, will be disposed of at the end of the study, according to standard laboratory procedures.

Where the patients opt to provide a buccal sample [Amendment 3], this will be tested via the genedrive *CYP2C19* ID Kit (Genedrive Diagnostics Ltd). This system is able to detect common pharmacogenetic variation in the *CYP2C19* gene from a buccal swab.

8.3. Prescribing Data Collection and Analysis

Prescribing data for participants from the IPTIP-I arm will also be collected from the discharge summary and from the inpatient prescription chart. This data will be collected by the study team via a dedicated collection tool, also built into the bespoke portal. This can be done at a later timepoint, after recruitment.

Following source data collection, with participant consent, study ID, identifiable demographic, and inpatient prescribing data will be shared with Graphnet CareCentric who operate the Greater Manchester Care Record (GMCR). These records will then be linked with outpatient prescribing data from within the GMCR and deposited as a pseudonymised dataset (labeled with study ID only) available for analysis by the research team within Graphnet's secure data analysis environment. Participant genotype will be then be added to the final dataset within the secure research environment, linked by the Study ID. The final pseudonymised dataset will contain study ID, medicine history, participant genotype and metabolizer status.

The GMCR joins together Greater Manchester's different NHS and care organisations to support hospitals and other care services access individual health and care records quickly and securely. Utilization of the GMCR for the IPTIP trial offers several unique advantages. Firstly, the near 'real-time' data availability enables access to up-to-date prescribing data from the primary care setting in a more reliable and accurate way than is available in other data sources. The data source also provides access to the historical prescribing data of any participant registered with a GP in the conurbation. There is precedent for research and data-sharing such as this using the GMCR and the Graphnet environment. At the time of writing, 15 studies have been approved using GM Care Record Data (https://gmwearebettertogether.com/research-and-planning/). Previously published studies using the GMCR have not sought written consent from participants as the datasets were fully deidentified. Here, as this project first collects the data using the GMCR, extracts it into the Secure

Data Environment known as the Analytics and Data Science Platform (ADSP) to makes use of pseudonymised data for analysis, we will seek consent from participants for data sharing, handling and analysis within a secure environment.

There will be some infrequent cases where access to the GMCR is not possible for participants, either because the individual has chosen to opt-out of involvement in the GMCR or, more likely, because they are not registered with a GP in Greater Manchester. In these cases, the research team will seek permission from the participants to manually access historical prescribing data via the Summary Care Record (SCR). With a participant's permission, the SCR can be viewed through internal MFT clinical systems or through the Summary Care Record application (SCRa) on the Spine web portal. These data will then be uploaded, alongside the study ID into the final analysis dataset within the secure research environment.

A schematic representation of the data collection, access and analysis process for this project is given in Appendix 1.

The recruitment proforma, containing the "key" to de-anonymize the final dataset, will be stored securely by the senior investigator, [name] for 5 years following the end of the study. After this, the key will be destroyed, rendering the dataset fully anonymous. There is no formal study intervention and participants will not be contacted after the initial enrolment. No participant specific results will be generated and fed back to the participants or their clinician(s).

